#### 4.6 **Premature Termination of the Trial**

For either cohort, the trial may be discontinued prematurely in the event of any of the following:

New information leading to unfavorable risk-benefit judgment of the IMP, for example, due to

1. Evidence of inefficacy of the IMP,

2. Occurrence of significant previously unknown adverse reactions or unexpectedly high intensity or incidence of known adverse reactions, or

3. Other unfavorable safety findings.

(Note: Evidence of inefficacy may arise from this trial or from other trials; unfavorable safety findings may arise from clinical or non-clinical examinations, for example, toxicology.)

- Merck/EMD Serono or the IND Office's decision that continuation of the trial is unjustifiable for medical or ethical reasons.
- Poor enrollment of subjects making completion of the trial within an acceptable time frame unlikely.
- Discontinuation of development of the Merck/EMD Serono's IMP.

Health Authorities and Independent Ethics Committees (IECs) / Institutional Review Boards (IRBs) will be informed about the discontinuation of the trial in accordance with applicable regulations.

The whole trial may be terminated or suspended upon request of Health Authorities.

### 4.7 **Definition of End of Trial**

If the trial is not terminated for a reason given in Section 4.6, the end of the trial is defined as 1 year after the last subject receives the last dose of M7824.

### 5 Investigational Medicinal Product and Other Drugs Used in the Trial

The term "Investigational Medicinal Product" (IMP) refers to an active substance or a placebo being tested or used as a reference therapy in a clinical trial, including products that have a marketing authorization but are formulated, packaged, or administered differently from the authorized form, used for an unauthorized indication, or used to gain further information about the authorized form. The only IMP used in this trial is M7824.

### 5.1 Description of the Investigational Medicinal Product

M7824 drug product is a sterile, freeze-dried formulation presented at a concentration of 600 mg/vial in United States Pharmacopeia (USP) type I glass vial closed with a rubber stopper and sealed with an aluminum plastic crimping cap.

Each vial contains 600 mg of M7824 as a preservative-free histidine-buffered solution (pH=5.5) containing trehalose dihydrate, sodium chloride, L-methionine and polysorbate 20 (Tween 20). Only excipients that conform to the current USP are used for M7824 drug product.

### 5.2 Dosage and Administration

#### 5.2.1 M7824 Administration

Subjects will receive IV infusion of M7824 over 1 hour (-10 minutes / +20 minutes) once every 2 weeks as detailed in the Schedules of Assessments (see **Tables 1-3**). Modifications of the infusion rate due to infusion-related reactions are described in Section 5.5.3.1.

The dose for M7824 is 1200mg. In cohorts A-C and B, subjects will receive M7824 once every 2 weeks until confirmed progression, unacceptable toxicity, or any criterion for withdrawal from the trial or IMP occurs (see Section 4.5). Subjects who have experienced a persistent, confirmed PR

or CR may continue treatment through the end of 12 months, although additional treatment is possible. If the Investigator believes that a subject may benefit from treatment beyond 12 months, it may be permissible after discussion with the principal investigator. In cohort D, patients will receive M7824 for 6 doses. After 6 doses, the patient will have blood checked for ctDNA clearance. If there is no evidence of radiographic or clinical progression, then the patient may continue on study at the discretion of the investigator.

For subjects who achieve a PR or CR on M7824 therapy and then subsequently develop disease progression after stopping therapy, but prior to the end of the trial, a re-initiation course of treatment at the same dose and schedule and treatment duration up to 12 months is allowed at the discretion of the Investigator and agreement of the trial principal investigator. Subjects re-initiating treatment should be assessed according to the Schedules of Assessment of the trial starting at Week 1, Day 1 (see **Tables 1-3**).

## 5.2.2 Radiotherapy (cohort B only)

Radiation therapy will be delivered to a single metastatic lesion, with total dose of 24 Gy in 3 daily fractions of 8 Gy each. Radiation therapy will be delivered on consecutive business days. All 3 fractions will be administered after the second dose of M7824 and prior to the administration of the third dose of M7824.

Patients will undergo CT simulation, with or without IV contrast. The gross tumor volume (GTV) will include a single metastatic lesion. The metastatic lesion to be irradiated must not be adjacent to a dose-limiting normal structure (e.g., heart, bowel) at the discretion of the treating radiation oncologist. The planning target volume (PTV) will include the GTV with a 5-7 mm margin in all directions. For lesions affected by respiratory motion, appropriate motion management techniques should be used, such as inspiratory breathhold. Daily volumetric imaging with cone beam CT (CBCT) or CT on rails (CTOR) will be used for image guidance.

### 5.3 Assignment to Treatment Groups

Not applicable

## 5.4 Noninvestigational Medicinal Products to be Used

In order to mitigate potential infusion-related reactions, premedication with an antihistamine (e.g., 25-50 mg PO at the discretion of the investigator) and with acetaminophen (e.g., 325-650 mg PO at the discretion of the investigator) approximately 30 to 60 minutes prior to each dose of M7824 is mandatory for the first 2 infusions and is optional and at the discretion of the Investigator starting with the third infusion. If Grade  $\geq 2$  infusion reactions are seen during the first two infusions, then premedications should not be stopped. Steroids as premedication are not permitted. Special precautions for monitoring of subjects and management of infusion-related reactions / hypersensitivity including modifications. As with all monoclonal antibody therapies, there is a risk of allergic reaction including anaphylactic shock. M7824 should be administered in a setting

that allows for immediate access to an intensive care unit or equivalent environment and administration of therapy for anaphylaxis, such as the ability to implement immediate resuscitation measures. Steroids (dexamethasone 10 mg IV), epinephrine (1:1,000 dilution), allergy medications (IV antihistamines), bronchodilators, or equivalents, and oxygen should be available for immediate access in the event of an anaphylactic reaction. Infusion of M7824 will be stopped in case of Grade  $\geq 2$  infusion-related, allergic, or anaphylactic reactions. Following M7824 infusions, subjects must be observed for a minimum of 2 hours post end of infusion for potential infusion-related reactions. Please see the guidelines for handling of infusion-related reaction in Section 5.5.3.1.

If an allergic reaction occurs, the subject must be treated according to the best available medical practice. Guidelines for management of infusion-related reactions and severe hypersensitivity reaction according to the National Cancer Institute are found in Section 5.5.3.

Further precautions are provided in Section 5.5.3.2. For prophylaxis of flu-like symptoms, a nonsteroidal anti-inflammatory drug (NSAID) for example, ibuprofen 400 mg or comparable NSAID dose, may be administered 2 hours before and 8 hours after the start of each dose of M7824 IV infusion.

### 5.5 Concomitant Medications and Therapies

All concomitant medications taken by the subject during the trial, from the date of signature of informed consent are to be recorded in the appropriate section of the eCRF (Prometheus) and medical record, noting the name, dose, duration and indication of each drug. Nondrug interventions (other than vitamins) and any changes to a concomitant medication or other intervention should also be recorded in the eCRF (Prometheus) and medical record.

#### 5.5.1 Permitted Medicines

Any medications (other than those excluded by the clinical trial protocol) that are considered necessary to protect subject welfare and will not interfere with the trial medication may be given at the Investigator's discretion.

Other drugs to be used for prophylaxis, treatment of anaphylactic reactions, infusion-related reactions, and severe hypersensitivity reactions / flu-like symptoms and irAEs are described in Section 5.5.3.

Palliative radiotherapy delivered in a normal organ-sparing technique may be administered during the trial. The assessment of PD will not be based on the necessity for palliative radiotherapy.

### 5.5.2 Prohibited Medicines

As stated for the exclusion criteria in Section 4.3.2, subjects must not have had chemotherapy, radiotherapy (other than palliative radiotherapy delivered in a normal organ-spearing technique as described in Section 5.5.1), major surgery, or received another investigational agent within 28 days before the start of trial treatment.

The following treatments must not be administered during the trial:

- Immunotherapy including interferon, immunosuppressive drugs (for example, chemotherapy or systemic corticosteroids except for short term treatment of allergic reactions, endocrine replacement therapy at low dose prednisone [≤ 10 mg daily] or equivalent, or for the treatment of irAEs or other appropriate short term steroid use), or other experimental pharmaceutical products. Short term administration of systemic steroid or other immunosuppressant such as infliximab or mycophenolate (that is, for allergic reactions or the management of irAEs) is allowed. Steroids with no or minimal systemic effect (topical, inhalation) are allowed. Note: for subjects with glioblastoma, steroid use is allowed.
- Adefovir.
- Prophylactic use of corticosteroids for infusion related reactions is prohibited.
- Any live vaccine therapies for the prevention of infectious disease. Administration of inactivated vaccines is allowed (for example, inactivated influenza vaccines).
- Blood transfusions and erythroid growth factors are permitted for Hgb  $\leq$  less 7 g/dL and/or for life threatening bleeding

If the administration of a non-permitted concomitant drug becomes necessary during the trial, the subject will be withdrawn from trial treatment (the Principal investigator may be contacted to discuss whether the IMP must be discontinued).

Medications other than those specifically excluded in this trial (as outlined in this section) may be administered for the management of symptoms associated with the administration of M7824 as required. These might include analgesics, anti-emetics, antihistamines, diuretics, anti-anxiety medications, and medication for pain management, including narcotic agents.

Any additional concomitant therapy that becomes necessary during the trial and any change to concomitant drugs must be recorded in the corresponding section of the eCRF (Prometheus) and medical record, noting the name, dose, duration, and indication of each drug.

The following non-drug therapies must not be administered during the trial (and within 28 days before the start of trial treatment):

- Major surgery (excluding prior diagnostic biopsy).
- Herbal remedies with immunostimulating properties (for example, mistletoe extract) or known
- to potentially interfere with major organ function (for example, hypericin)
- Subjects should not abuse alcohol or other illicit drugs during the trial

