# 4.1.4.2 Adverse Drug Reactions Requiring Treatment Discontinuation

# The following ADRs, defined as any AE assessed as related to M7824 by the Investigator and / or Merck/EMD Serono, require permanent treatment discontinuation:

Any Grade 4 ADRs require treatment discontinuation except for single laboratory values out of normal range that do not have any clinical correlate, and resolve to Grade  $\leq 1$  or Baseline grade within 14 days with adequate medical management.

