#### Any Grade 3 ADRs require treatment discontinuation except for any of the following:

- Transient (≤ 6 hours) Grade 3 flu-like symptoms or fever, which is controlled with medical management.
- Transient ( $\leq 24$  hours) Grade 3 fatigue, local reactions, headache, nausea, emesis that resolves to  $\leq$  Grade 1 or Baseline grade.
- Tumor flare phenomenon defined as local pain, irritation, or rash localized at sites of known or suspected tumor.
- Any Grade ≥ 3 drug-related amylase or lipase abnormality that is not associated with symptoms or clinical manifestations of pancreatitis. The study principal investigator should be consulted for such Grade ≥ 3 amylase or lipase abnormalities. If the amylase or lipase abnormality not associated with symptoms or clinical manifestations of pancreatitis has not resolved to Grade ≤ 1 within the subsequent 2 doses (28 days), the subject should permanently discontinue treatment with M7824.
- Grade 3 Hgb decrease (< 8.0 g/dL) that is clinically manageable with blood transfusions or erythroid growth factor use does not require treatment discontinuation.
- Increases in Eastern Cooperative Oncology Group performance status (ECOG PS) ≥ 3 that resolves to ≤ 2 by Day 1 of the next cycle (infusions should not be given if the ECOG PS is ≥ 3 on the day of IMP administration and should be delayed until ECOG PS ≤ 2).

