### 4.5 Criteria for Subject Withdrawal

#### 4.5.1 Withdrawal from Trial Treatment

Subjects will be withdrawn from trial treatment for any of the following reasons:

- PD as defined by iRECIST 1.1
  - Patients may continue on M7824 until immune confirmed PD (iCPD) provided they meet the criteria for pseudoprogression (see 5.5.1.1 below)
- Therapeutic failure requiring urgent additional cancer therapy
- Occurrence of any Grade ≥ 3 ADRs or repetitive Grade 2 ADRs as defined in Section 5.5.3.3.
- Occurrence of AEs, at the Investigator's discretion
- Pregnancy
- Use of prohibited concomitant drug, as defined in Section 5.5.2, where the predefined consequence is withdrawal from the IMP
- Non-adherence / non-compliance to the trial protocol or trial requirements (see Section 5.9)
- Withdrawal of consent
- Participation in any other trial

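### Sections 4.1.4.2 and 5.5.2 conflict on growth factor or transfusion for drug-related Grade 3 anemia with hemoglobin above 7 and below 8.0 g/dL

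*Combined protocol and SAP*

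**What the plan says.** **Section 4.1.4.2** concerns adverse drug reactions, "defined as any AE assessed as related to M7824 by the Investigator" or the drug supplier. Grade 3 reactions lead to permanent discontinuation, with listed exceptions. One exception is a Grade 3 hemoglobin decrease, put at below 8.0 g/dL, "that is clinically manageable with blood transfusions or erythroid growth factor use does not require treatment discontinuation". The same section later refers anemia to Section 5.5.3.4.

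**Section 5.5.2**, Prohibited Medicines, opens its list with "The following treatments must not be administered during the trial". The last bullet reads "Blood transfusions and erythroid growth factors are permitted for Hgb" and, after a less-than-or-equal sign, "less 7 g/dL and/or for life threatening bleeding". Below the list comes the consequence: "If the administration of a non-permitted concomitant drug becomes necessary during the trial, the subject will be withdrawn from trial treatment". A parenthesis adds that "the Principal investigator may be contacted to discuss whether the IMP must be discontinued".

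**Section 4.5.1** lists as a reason for stopping treatment: "Use of prohibited concomitant drug, as defined in Section 5.5.2, where the predefined consequence is withdrawal from the IMP".

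**Section 5.5.3.4**, Anemia, has the investigator consider a work-up at hemoglobin below 8 g/dL, with close monitoring. Its evaluation table leaves transfusion to clinical discretion when hemolysis or bleeding is suspected. It gives no hemoglobin limit for transfusion and does not mention growth factor as a treatment.

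**Section 5.5.1** allows medication needed for the patient's welfare, but not medication that the protocol excludes.

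**The concern.** The exception in 4.1.4.2 rests on a treatment being usable, and 5.5.2 withholds that treatment over part of the range the exception covers. A physician with a symptomatic patient at 7.5 g/dL could read 4.1.4.2 and 5.5.3.4, treat, and continue M7824. The same physician could read 5.5.2 and conclude that the treatment is not permitted and that needing it means stopping M7824.

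At stake are supportive care and continued access to study drug for a recognised risk. Section 6.4.1.1.3 makes drug-related anemia an adverse event of special interest at every grade. That is a reporting rule and does not decide how the patient is treated, but it shows that the event is one the plan expects to handle. No effect on an endpoint, on the toxicity stopping rule or on an analysis is claimed.

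**Working it through.** The plan states no figure to reproduce here. The check sets the rules side by side.

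**Where they overlap.** Section 4.1.4.2 covers hemoglobin below 8.0 g/dL. Section 5.5.2 permits treatment at about 7 g/dL or lower, or for life-threatening bleeding. The range covered by the first and not by the second is 7 < Hgb < 8.0 g/dL without such bleeding.

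**Cases**, all with a drug-related Grade 3 decrease and no life-threatening bleeding:

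| Patient | Section 4.1.4.2 | Section 5.5.2 | Do they fit? |
|---|---|---|---|
| 7.5 g/dL, stable, no treatment needed | No forced stop | Nothing non-permitted is needed | Yes |
| 7.5 g/dL, needs growth factor | No forced stop, because the event is manageable that way | Not permitted by implication; withdrawal by default | No, on permission and on continuation |
| 7.5 g/dL, needs transfusion | No forced stop, for the same reason | Not permitted by implication; withdrawal unclear, since the sentence says drug | No on permission; unclear on continuation |
| 6.9 g/dL, needs either | No forced stop | Permitted | Yes |

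Rows two and four show an inversion: the less anemic patient who needs growth factor faces default withdrawal, and the more anemic one does not. This suggests that the two thresholds were not reconciled.

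**Does other text settle it?**
- Section 5.5.1 does not, because its welfare clause stops at what the protocol excludes.
- Section 5.5.3.4 comes closest. It is the section to which 4.1.4.2 refers for anemia, and it sets no 7 g/dL limit. But its transfusion guidance sits in two rows only (suspected hemolysis, suspected bleeding), it does not cover growth factor as treatment, and it claims no precedence over 5.5.2.
- The principal-investigator clause in 5.5.2 is optional. It addresses whether M7824 must stop, without saying which section controls or whether the treatment may be given.

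**Does the event occur?** Section 2.1.1 reports drug-related Grade 3 anemia in 1 of 32 patients in the 1,200 mg colorectal expansion cohort and in 1 of 19 in dose escalation at mixed doses. With exact (Clopper-Pearson) 95% intervals:
- 1/32 = 3.1% (0.08% to 16.2%)
- 1/19 = 5.3% (0.13% to 26.0%)

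Both counts include any hemoglobin value that was graded 3. They show that the event happens; they do not size the 7 to 8 g/dL band.

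**The case against.** The strongest reply is that the sections can be applied together. Section 4.1.4.2 removes one ground for stopping; it orders neither transfusion nor continuation. Section 5.5.2 then says when treatment may be given. Anemia has its own section, 5.5.3.4, reached by a direct cross-reference, and preferring the specific section to a general medication list is ordinary practice. The cross-reference does stand among the Grade 2 bullets, but its neighbour covers Grades 1 to 4. The 5.5.2 bullet is phrased as a permission, the withdrawal sentences in 5.5.2 and 4.5.1 speak of a drug, and the principal investigator can be asked in a trial run within one department.

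Much of this stands, and it rules out three stronger readings that a reader might infer:
- **That every patient in the band receives contradictory instructions.** A stable patient who needs no treatment satisfies both sections.
- **That a transfusion in the band clearly triggers withdrawal.** The word drug fits growth factor plainly and blood much less so.
- **That the protocol is otherwise silent.** Section 5.5.3.4 does speak to transfusion, without the 7 g/dL limit.

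What the reply does not remove is the case of a patient who needs treatment. A permission with a threshold, placed in a list of prohibited treatments, does nothing unless use beyond the threshold is barred. For that patient the 4.1.4.2 exception relies on a treatment that 5.5.2 withholds. Section 5.5.3.4 differs from 5.5.2 on transfusion without overriding it, and leaves growth factor unaddressed.

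**Conclusion.** The conflict holds in a narrow form: wrong as written, and minor. It applies to a patient with drug-related Grade 3 anemia, hemoglobin above 7 and below 8.0 g/dL, no life-threatening bleeding, and a need for treatment. For growth factor, the sections disagree on whether it may be given and on whether M7824 continues. For transfusion, they disagree on whether it may be given; what follows for M7824 is less clear.

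Two assumptions carry this. The bar above 7 g/dL is inferred from the bullet's place in the prohibited list, since no sentence states it. The threshold is read as 7 g/dL; the stray word beside the sign may come from text extraction and is not counted as an error.

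The number of patients affected is unknown and probably small. A reader might take 3.1% or 5.3% as the expected share in this trial. The documents do not support that, because they give no hemoglobin values for those events.

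**What to change.** Amend the 5.5.2 bullet so that transfusion or erythroid growth factor is also permitted, at clinical discretion, for the Grade 3 hemoglobin decrease (below 8.0 g/dL) that 4.1.4.2 exempts and 5.5.3.4 manages, and keep the permission for life-threatening bleeding. State there that such use does not trigger withdrawal under 5.5.2 or 4.5.1, and tidy the threshold wording in the same edit.

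If the sponsor intends a restrictive 7 g/dL limit, narrow the 4.1.4.2 exception and align 5.5.3.4 with it instead. The documents do not show which was intended, so the sponsor must choose.

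The cost is wording only: one bullet in 5.5.2 with a cross-reference in 4.5.1, or matching edits to 4.1.4.2 and 5.5.3.4. No new data or procedures are needed.

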### 5.5.3 Special Precautions

As a routine precaution, subjects all enrolled in this trial must be observed for 2 hours in the CTRC post end of infusion, in an area with resuscitation equipment and emergency agents at least for the first two doses of treatment with M7824. If no medical problems arise during the first two treatments, then the 2 hour observation period does not need to continue starting with the third dose of treatment. At all times during M7824 treatment, immediate emergency treatment of an infusion-related reaction or a severe hypersensitivity reaction according to institutional standards must be assured. In order to treat possible anaphylactic reactions, for instance, dexamethasone 10 mg and epinephrine in a 1:1000 dilution or equivalents should always be available along with equipment for assisted ventilation.

Infusion of M7824 will be stopped in case of Grade  $\geq 2$  hypersensitivity, inflammatory response, or anaphylactic reaction. The treatment recommendations for infusion-related reactions and severe hypersensitivity reactions according to the NCI are outlined in Sections 5.5.3.1 and 5.5.3.2, respectively.

Investigators should also monitor subjects closely for potential irAEs (described in Section 5.5.3.3), which may become manifest after several weeks of treatment. Such events may consist of persistent rash, diarrhea and colitis, autoimmune hepatitis, arthritis, glomerulonephritis, cardiomyopathy, or uveitis and other inflammatory eye conditions.

